2.1 Treatments

Each subject watches three videos. Each video features a different doctor. All partner doctors viewed in the videos by a given subject are of the same racial or ethnic background.²

1. Video 1:

- Introduction
- Discussion of symptoms
- Acknowledgement of “elephant in the room” issues, where applicable.

2. Video 2:

- Information about social distancing and hygiene

3. Video 3:

- Information about masks

We are varying four aspects of the videos across treatments:

1. Racial or ethnic concordance with partner doctors in the videos (note that we side-step the issue of language: for Spanish speakers, they can chose English or Spanish, and there are non ethnically Hispanic doctors speaking in Spanish).³
2. Video 1 content: Elephant in the room
 - No elephant in the room content
 - Elephant in the room 1: Trust or Fear
 - Elephant in the room 2: Economic Inequality

²However, some individuals may see two black doctors and [name] from the CDC, a white doctor and representative of the US government.

³However we do not have recordings in other languages.

3. Identity of the doctor delivering Video 2

- Pre-recorded video of [name] of the CDC in front of the White House
- Partner doctor

4. Video 3 content: mask debiasing

- Basic mask information, no perceptions information
- Basic mask information, perceptions information
 - For the latinx community, the video discusses perceptions that the mask-wearer is sick.
 - For the black community, the video discusses perceptions that the mask-wearer is “up to no good.”
 - In both cases the message reports responses from a prior survey of perceptions that mask wearers in photos of the same racial/ethnic group are “protecting the community.”

All of the video scripts can be found in Appendix Section A. Figure 1 shows how these different treatments are incorporated in the randomization design.

Figure 1: Treatment Design: There are 8 content-variants for each video, shown here. Cell 1c/d includes the baseline information package. For each combination of message content, the partner doctors in the video may either be of a concordant (c) or discordant (d) racial/ethnic background.

All treatments receive basic information +	Doctor-Delivered CDC Message	[name] -Delivered CDC Message	Elephant 1: Fears (L) or Trust (A)	Elephant 2: Economic Inequality
No Mask Debiasing	1c/d	2c/d	3c/d	4c/d
Mask Debiasing	5c/d	6c/d	7c/d	8c/d

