2.3 Experimental Protocols and Treatments

Our experiment has the following structure:

1. Recruitment and Baseline survey
 - (a) Recruit target sample via Lucid
 - (b) For Hispanic respondents, elicit a preference for English or Spanish. Those with a preference for Spanish will be given Spanish language survey questions and will see treatment videos recorded in Spanish as well.⁴
 - (c) Collect demographic information and healthcare experience. Several demographics variables are being collected directly by Lucid.
2. Randomize Subjects to treatment
 - Treatment scripts are tailored to each racial/ethnic group
 - Within racial/ethnic group, treatment is stratified on age, gender and geographic region.
 - Randomization is at the individual level according to Figure 1.
 - There will also be a control group who will receive COVID-19 information at the very end of the survey.
3. Video delivery for all individuals not in the pure control group.
 - (a) After each of the three videos, respondents evaluate the video's usefulness, and trustworthiness, along with the respondents intention to follow the advice in the video and share information from the video.
 - (b) Prior to the third video (masks), individuals will answer questions about second order beliefs about mask wearers.
4. Endline survey
5. Videos shown to the pure control group.
6. Debrief script
7. Follow-up survey
 - (a) We are tentatively planning to follow up with participants several days post-treatment
 - (b) The chief purpose would be to measure health-seeking and health-preserving behaviors.⁵
8. Once we learn which messaging strategy is most effective, we will scale up that treatment more broadly (distributing it through social media etc.)

⁴The one exception is the CDC video with [name]. This is always shown in English.

⁵We do not commit on analyzing this data or even fully implementing a follow up because it is quite difficult to successfully follow up with online survey participants, so it will depend on our success in finding people in our pilot.

3. General Hypotheses to be Tested

This section lists the general hypotheses we want to test. For those, we are planning to run broadly pooled treatments (and specific interactions specified below).

Main hypotheses:

1. What is the overall effect of any combination of videos, compared to the control group?
2. Does racial concordance between the doctor messenger and recipient give the message higher impact across the board?

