5.3 Regression Analysis

We will do two types of analysis: identifying effective videos in our sample, and general tests of the hypotheses described above.

- Best treatment

We are interested in selecting the best combination of types of video for scale up. In order to identify the most effective combination of videos, we will adapt a disciplined pooling methods of Banerjee et al (2020) for selecting the most effective combination of treatments (to a settings were we have large

sample within each of 16 treatment cells), and Andrews et al (2020) to correct for small sample bias in estimating the impact the most effective method.⁶

For this specific question of whether *our* messages of a given type (concordant race, correcting priors, etc), since random assignment is done by individuals, we do not adjust standard errors. This is the correct analysis for scaling up these videos per-se.

- Hypothesis tests

In order to test the hypotheses listed above, we run the following contrasts (Hispanic and Black will be run separately for all the contrasts:

Main hypotheses tests:

1. Is there any impact of the videos (treatment vs control)
2. Concordant vs. discordant messengers: pooled across all
3. [name] with "no elephant" and the two different versions of "elephant in the room", no [name] each compared to the "no elephant, no [name]" condition
4. [name] versus everything else.
 - For social distancing and hygiene (largest effect expected here for the [name] treatment)
 - For other outcomes
5. Mask-debiasing treatment on mask outcomes, heterogenous based on respondent prior beliefs (lower or higher than 8 out of 10 people think mask wearer is helping the community).

Secondary hypotheses tests

1. [name] treatment effects will be interacted with concordant doctor
2. [name] treatment effect will be interacted with social debiasing treatment (which may be less effective after presenting [name])
3. Elephant treatment will be interacted with concordant doctor
4. Mask treatment effect will be interacted with concordant doctor
5. Mask treatment effect will be interacted with elephant treatment
6. [name] treatment effect will be interacted with elephant treatment
7. Gender of provider will be interacted with concordant doctor and/or respondent gender

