Everywhere, we will control for the strata, race/ethnicity, and where applicable, choice of English versus Spanish. Robustness of results to any possible chance unbalance will be checked by running the Belloni et al. Lasso procedure to select control variables.

⁶Banerjee, Abhijit, Arun Chandrasekhar, Esther Duflo, Matthew O. Jackson, John Floretta, Harini Kannan, Francine Loza, Anirudh Sankar, and Anna Schrimpf (2020) "Selecting the most effective nudge: evidence from a large scale experiment on immunization," Working Paper.)

For this more general analysis of whether a given type of video is more effective in general, one may want to consider a hypothetical where the videos we use were drawn from a larger pool of possible videos (i.e. we recruited N doctors but could have recruited $2N$ doctors from the same pool). In this broader exercise, one also wants to adjust standard errors to account for the possible doctor-video random effect. We will develop and implement the correct methods to do so.

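### The mask-debiasing tests leave out the Video 1 and Video 2 ratings, which treated respondents give before debiasing is shown: a loss of precision of unknown size, not a bias

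*Combined protocol and SAP*

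**What the plan says.** - **Controls.** Section 5.3: "Everywhere, we will control for the strata, race/ethnicity, and where applicable, choice of English versus Spanish". The only other covariate step is a sensitivity check: "Robustness of results to any possible chance unbalance will be checked by running the Belloni et al. Lasso procedure to select control variables". No list of candidate variables is given for it.
- **When ratings are taken.** Section 2.3, step 3(a): "After each of the three videos, respondents evaluate the video's usefulness, and trustworthiness". The same step has them say whether they mean to act on the advice and to pass the information on. Step 3 is headed "Video delivery for all individuals not in the pure control group", so the pure control group has no such answers before its endline.
- **Where debiasing appears.** Section 2.1, item 4, is titled "Video 3 content: mask debiasing". Appendix A shows it as an optional segment (3B) inside Video 3. Figure 1 crosses it with the four message columns and with concordance, and section 2.3 randomizes individuals.
- **Tests affected.** Main test 5 in section 5.3: "Mask-debiasing treatment on mask outcomes, heterogenous based on respondent prior beliefs". Secondary tests 2, 4 and 5 interact debiasing with the CDC video, with concordance and with the elephant content.
- **Role given to the ratings.** Section 5.2 uses them as family 1 outcomes. No section uses them as covariates.

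**The concern.** Debiasing differs from the other randomized factors in timing. Concordance and the elephant content act from Video 1, and the CDC video replaces Video 2. By the time debiasing is shown, each treated respondent has already answered on usefulness, trust, sharing and intention for two videos. For the debiasing contrast, and only for that contrast, these answers work as a baseline measure of general receptiveness.

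The plan already relies on this timing. Beliefs about mask wearers are elicited just before Video 3, after Videos 1 and 2, and main test 5 uses them as a pre-exposure modifier.

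Precision is at stake. The debiasing tests are run separately for Black and Hispanic respondents, split by prior belief or interacted with another factor, and then adjusted for multiple outcomes. They are among the thinner comparisons in the plan.

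**Working it through.** **The plan's own figures.** There is no power calculation, effect size, alpha or standard deviation to reproduce. The counts agree: 10,000 + 5,000 = 15,000 respondents (section 2.2), and 8 content variants × 2 concordance levels = 16 cells (Figure 1, section 5.3).

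**Assumptions, since the plan is silent.** Pure control share 1/17 (17 equal arms); debiasing allocated 1:1; outcome SD 1; two-sided 5% before multiplicity adjustment; 80% power; target sample sizes before the exclusions in section 4.2; no doctor-video random effect. Treated N is 10,000 × 16/17 ≈ 9,412 (Black) and 5,000 × 16/17 ≈ 4,706 (Hispanic).

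**Formulas.**
- Minimum detectable effect (MDE), pooled debiasing effect: (1.960 + 0.842) × 2/√N.
- MDE, debiasing × concordance: (1.960 + 0.842) × 4/√N.
- Adjustment multiplies the variance by 1 − r² and the MDE by √(1 − r²). Here r is the partial correlation of the ratings with the outcome, given the planned controls.
- Equivalent gain in sample size: 1/(1 − r²) − 1.

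**Unadjusted results.** Main effect: 2.802 × 2/√9,412 = 0.058 SD (Black) and 2.802 × 2/√4,706 = 0.082 SD (Hispanic). With a control share from 0 to 20%, the ranges are 0.056–0.063 and 0.079–0.089.

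**Adjusted results.**

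| r | Variance cut | Equivalent N | MDE main, Black / Hispanic | MDE × concordance, Black / Hispanic | Power where unadjusted is 80% |
|---|---|---|---|---|---|
| 0.1 | 1% | +1.0% | 0.0575 / 0.0813 | 0.115 / 0.163 | 80.4% |
| 0.2 | 4% | +4.2% | 0.0566 / 0.0800 | 0.113 / 0.160 | 81.6% |
| 0.3 | 9% | +9.9% | 0.0551 / 0.0779 | 0.110 / 0.156 | 83.6% |
| 0.4 | 16% | +19.0% | 0.0529 / 0.0749 | 0.106 / 0.150 | 86.4% |
| 0.5 | 25% | +33.3% | 0.0500 / 0.0707 | 0.100 / 0.142 | 89.9% |

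These are pooled effects. Main test 5 compares respondents below and above the prior-belief cut. With a share p below the cut, the variance of that difference is 4/(Np) + 4/(N(1 − p)) = 4/(Np(1 − p)). This is 16/N at p = 0.5, as for the concordance interaction, and larger for an uneven split. The percentage cut in variance is again r², with r taken for that model.

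**Check for bias.** A simulation used 2,000 runs with n = 4,706. The rating depended on concordance, CDC video and elephant content, and its partial correlation with the outcome was about 0.40. The true concordance, CDC and elephant interactions with debiasing were 0.074, −0.066 and 0.062.

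| Debiasing term | Mean, unadjusted → additive | Empirical SE, unadjusted → additive |
|---|---|---|
| Main (reference cell) | 0.102 → 0.101 | 0.0658 → 0.0601 |
| × concordance | 0.073 → 0.072 | 0.0580 → 0.0531 |
| × CDC video | −0.066 → −0.065 | 0.0839 → 0.0758 |
| × elephant | 0.062 → 0.062 | 0.0719 → 0.0646 |

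The debiasing terms are unchanged and their standard errors fall by about 8–10%. Two things go wrong if the adjustment is careless:
- In the same additive model the concordance coefficient moved from 0.099 to −0.025, because the ratings come after that factor.
- Adding a debiasing × raw-rating term moved the concordance interaction from 0.073 to 0.049.

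Centering the rating within concordance/CDC/elephant cells avoided both and kept the gain.

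**The case against.** The strongest reply is that nothing in the plan is wrong. Under individual randomization the planned contrasts are unbiased without these covariates, and adding them is an efficiency choice. That stands. A reader might infer that the debiasing estimates are confounded or invalid; nothing in the documents supports that.

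The second reply concerns size. A reader might treat the ratings as a baseline of the outcome itself, assume r = 0.5, and claim about 12 points of power: for a 0.05 SD effect in Black respondents, SE = √(2/4,706) = 0.0206 and power rises from 68% to 80%. The documents do not support this. Section 5.2 puts the ratings in family 1, marked (T), whereas main test 5 is on the (M) outcomes: mask knowledge, views, interest in information and allocations. Hypothesis 6 in section 3 names information demand and money allocations. None of these repeats a Video 1 or Video 2 rating. At r = 0.2 the same example gains less than 2 points, and at 0.10 SD the unadjusted test already has 99.8% power (Black) or about 93% (Hispanic). The examples also leave out multiplicity adjustment, data-quality exclusions and the doctor-video random effect, which respondent-level covariates need not reduce. The pre-Video 3 mask beliefs may already carry some of the same information.

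Third, the Lasso might select the ratings. A reader might infer from the baseline variables listed for balance tests in section 5.1 that it cannot, but section 5.3 gives no candidate list, so this is open. It remains a robustness check, and the main specification still omits the ratings.

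**Conclusion.** The point holds as a cheap, optional improvement in efficiency. The ratings are collected before debiasing is shown, cannot be affected by it, and are absent from the planned controls. Additive adjustment leaves the debiasing coefficient and its interactions unbiased and multiplies their variance by 1 − r². The gain runs from negligible at r = 0.1 to substantial at r = 0.5, and the documents give no basis for choosing a value. It should be described as conditional on r, with no figure promised. The conclusion rests on the order of videos and ratings in section 2.3 and on individual randomization of debiasing. The detectable effects rest also on the assumed control share, unit SD and unadjusted 5% level.

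**What to change.** In section 5.3, for main test 5 and secondary tests 2, 4 and 5, state that:

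1. The models are fitted among treated respondents only. The pure control group has no ratings before endline, so a missing-rating indicator would otherwise mostly mark control status.
2. The Video 1 and Video 2 ratings (usefulness, trust, sharing, intention to follow the advice) enter as additive covariates, or centered within concordance/CDC-video/elephant cells, with an indicator for a missing rating and no debiasing × raw-rating term.
3. Only the debiasing coefficient and its interactions are read from these models.
4. The ratings are not used in models that estimate concordance, elephant or CDC-video main effects, nor where the outcome index itself contains Video 1 or Video 2 ratings. Secondary tests 2, 4 and 5 name no outcome, so this exclusion needs to be explicit.

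The cost is a short paragraph and one further set of regressions on data already collected. The downside is that the debiasing models carry a different covariate set from the other contrasts.

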5.4 Heterogeneous Effects

We are interested in understanding differences by baseline characteristics. We believe that there may be heterogeneous treatment effects based many dimensions. The three most important heterogeneous treatment effects are the following:

1. Heterogeneity in the effectiveness of the mask treatment by prior beliefs (i.e. whether people would update up or down from their priors based on the message seen).
2. Heterogeneity by gender, especially for understanding impacts on masks. (Our background research suggests that African American men feel mask stigma most strongly.)
3. Heterogeneity by language choice within the Latinx group (in particular for CDC message which is not translated)

We are also interested in exploring heterogeneity on the following categories of traits/characteristics.

- Vulnerability to Covid-19 (age, essential worker status, pre-existing health conditions)
- Level of baseline knowledge (education, prior interaction with the health-care system, information sources)
- Location effects (covid-19 policies, covid-19 infection rates, and socio-economic conditions)

Given the many ways to cut the data we will follow the methodology of Chernozhukov et al (2018) for this latter set of potential heterogeneous treatment effects.⁷

6. Robustness

6.1 Threats to Interpretation

We would like to assume that differences across videos come from either differences in the racial/ethnic identity of the doctors in the video or from differences in the content of the messages, rather than from other chance differences across videos. We are considering doing a separate round of surveys where respondents watch portions of the videos common to all treatments and rate them on characteristics such as production quality, voice quality, voice appeal, and attractiveness. We would do this exercise following completion of the main experiment.

⁷Chernozhukov, Victor, Mert Demirer, Esther Duflo, and Ivan Fernandez-Val (2019). Generic machine learning inference on heterogenous treatment effects in randomized experiments. No. w24678. National Bureau of Economic Research.

6.2 Attrition

All baseline and endline outcomes will be obtained in the same online survey instrument. Attrition will be defined as those who have viewed the video but then drop out of the survey before completing it or have to be removed due to low quality video. We will check that attrition is not differential across study arms.

7. Funding and Human Subjects Review

Funding is provided by the National Science Foundation RAPID-2029880 for Covid-19 research, and RAI Italian Broadcasting corporation (via an unrestricted gift to J-PAL that we attributed to this project). The IRB at MIT is serving as the primary institution of record and has entered into a reliance agreement with Harvard, Massachusetts General Hospital, and Yale. We have also received IRB approval from Stanford.

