In addition to testing these hypotheses, we will also explore what is the most effective combination of messages and messengers overall (after “smart statistical pooling” of variants that prove similar), and what is its effect, accounting for any small sample bias induced by picking a winner.

4. Data Collection and Outcomes

We will run our experiment beginning on May 13, 2020. The data will be collected from respondent surveys. There is a short baseline module before the treatment group views the videos. Before the mask video (video 3), we elicit beliefs about perceptions of mask wearers. Then following video 3, there is an endline outcome module that all participants complete. (The control group only sees the videos after the endline has been completed.) We may decide at a later date to do a follow up survey with a subsample of the original participants. (Clearly, for this exercise, there will no longer be a valid control group. All comparisons will be done across treatments.) All of the survey responses will be downloaded is a .csv file for cleaning and analysis in STATA.

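### Section 6.2 counts drop-out only after a video has been viewed, but controls see theirs after the endline, so early control quitters go uncounted and treated and control rates are not comparable

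*Combined protocol and SAP*

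**What the plan says.** All places are in the combined protocol and SAP.

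- Section 6.2 gives the definition: "Attrition will be defined as those who have viewed the video but then drop out of the survey before completing it". A second limb adds those who "or have to be removed due to low quality video". The section then commits to a check: "We will check that attrition is not differential across study arms". It neither excepts the control group nor gives it a definition of its own.
- Section 2.3 sets the order of steps. Assignment is step 2, videos for the treated step 3, and the endline step 4. Step 5 is "Videos shown to the pure control group" and step 6 is "Debrief script". On the control group it says: "There will also be a control group who will receive COVID-19 information at the very end of the survey".
- Section 4 confirms the order: "The control group only sees the videos after the endline has been completed".
- Section 3 lists as its first main hypothesis: "What is the overall effect of any combination of videos, compared to the control group". Section 5.3 makes treatment versus control its first contrast and runs the Black and Hispanic samples separately.
- Section 4.2 is a separate check on low-quality responses. It does not deal with drop-out.

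**The concern.** An attrition check asks whether outcomes go missing at different rates in the groups being compared. The rule in Section 6.2 is conditioned on exposure to a video, and exposure falls before the outcome in the treated arms and after it in the control arm. The recorded control rate therefore carries no information about missing control outcomes.

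The contrast most exposed is main hypothesis 1. It also has an obvious reason for unequal loss, because only treated participants watch and rate three videos before they reach the endline. Section 6.2 is the only drop-out check that the plan states. If it fails for this contrast, a reader of the results cannot tell whether the treated and control groups with outcomes are still comparable.

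**Working it through.** The plan states no attrition figure, so there is none to reproduce. The argument is one of definition; the arithmetic only illustrates it.

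**Step 1. Apply the drop-out limb to each exit point** (order of steps from Sections 2.3 and 4).

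| Exit point | Treated: outcome; counted? | Control: outcome; counted? |
|---|---|---|
| After assignment, before viewing any video and before the endline is finished | Missing; no | Missing; no |
| After viewing, before the endline is finished | Missing; yes | Cannot occur |
| After the endline, before the control videos | Not applicable | Recorded; no |
| After the endline and after viewing, before the survey ends | Recorded; yes | Recorded; yes |

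Every control drop-out that loses an outcome falls in the first row, which is not counted. The only control drop-outs that are counted have outcomes.

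**Step 2. Illustration: inputs.**
- From the documents: N = 10,000 Black and 5,000 Hispanic (Section 2.2); 16 video cells (Section 5.3).
- Assumed, because the documents do not give them: control share 1/17 (17 equal arms); true loss before outcome dT (treated) and dC (control); c, the rate at which controls who reach their own videos then quit. *Viewed* is taken as started, with no treated loss before Video 1 and none between endline and end of survey. Rates are per person who viewed. Quality removals are left out.

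Control n = N/17, which is 588 and 294; treated n is 9,412 and 4,706. The treated rate under Section 6.2 is dT. The control rate is c, among N/17 × (1 − dC) people. So dC does not enter the control rate. Counts are rounded; p values are two-sided Fisher exact, Black / Hispanic.

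**Step 3. Equal true loss, dT = dC = 8%.** Treated: 753/9,412 and 376/4,706. Controls reaching their videos: 588.2 × 0.92 = 541 and 294.1 × 0.92 = 271.
- c = 0: 8.0% vs 0% (0/541, 0/271), p = 2e-19 / 7e-10.
- c = 2%: 11/541 and 5/271, p = 6e-9 / 3e-5.
- c = 6%: 32/541 and 16/271, p = 0.08 / 0.25.

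The true difference is zero throughout.

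**Step 4. Treated lose more, dT = 8%, dC = 3%.** Controls reaching their videos: 588.2 × 0.97 = 571 and 294.1 × 0.97 = 285. Counted from randomisation: 753/9,412 vs 18/588 and 376/4,706 vs 9/294, p = 2e-6 / 0.001. Under Section 6.2:

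| c | Control counts | p, Black / Hispanic |
|---|---|---|
| 0 | 0/571, 0/285 | 1e-20 / 2e-10 |
| 2% | 11/571, 6/285 | 1e-9 / 5e-5 |
| 4% | 23/571, 11/285 | 3e-4 / 0.008 |
| 5% | 29/571, 14/285 | 0.010 / 0.07 |
| 6% | 34/571, 17/285 | 0.08 / 0.26 |
| 8% | 46/571, 23/285 | 0.94 / 0.91 |
| 10% | 57/571, 28/285 | 0.10 / 0.26 |

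The check flags the correct arm in both samples up to c = 4%, and misses in both for c of about 6% to 10%. At c = 8% with control shares of 5% and 20%, its p is 0.93 to 1.0, against 0.0034 or less from randomisation.

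**Step 5. Controls lose more, dT = 3%, dC = 8%.** From randomisation: 282/9,412 vs 47/588 and 141/4,706 vs 24/294, p = 1e-8 / 3e-5. Under Section 6.2 at c = 0: 3.0% vs 0% (0/541, 0/271), p = 2e-7 / 5e-4, with the treated arm flagged. At c = 3%: 16/541 and 8/271, p = 1.0 / 1.0.

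**Step 6. Contrasts among the 16 video cells.** Here the effect depends on wording left open: each subject watches three videos (Section 2.1), yet Section 6.2 speaks of one. If *viewed* means started, little arm-related loss is missed. If it means finished, drop-out during Video 1 is missed; if all three must be finished, drop-out during Videos 2 and 3 is missed too.

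**The case against.** The strongest reply is that *study arms* may mean the video cells alone. The definition fits only people shown a video before the endline, and the plan elsewhere calls the comparator a control group. The text does not settle this. On that reading Section 6.2 gives no misleading treated-versus-control result, but only because it gives none, and main hypothesis 1 is left without a drop-out check.

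A reader might infer that no control with a missing outcome is ever counted. The documents do not support that. If the second limb was meant to cover low-quality responses, as in Section 4.2, some removed controls would be counted. It still does not bring in controls who quit early.

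A reader might also infer that the check will generally hide or reverse a real imbalance. Step 4 shows otherwise: where the treated lose more, which is the direction the design suggests, the check points to the correct arm unless c is fairly close to the treated loss. The reversal in Step 5 needs controls to lose more, and nothing in the documents suggests that. A control rate of exactly 0% would probably be recognised as a product of the survey order.

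Finally, baseline and endline share one instrument (Section 6.2) and assignment precedes the videos, so a count from randomisation should be recoverable later, and the analysts may have intended one. That stands, and it limits the harm. But a pre-analysis plan is meant to fix such choices before the data are seen, and the written rule says something else.

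**Conclusion.** The definition is wrong as written for main hypothesis 1. That conclusion rests only on the definition and the order of steps, with no assumed number. Depending on what *study arms* covers, the treated-versus-control check either compares unlike quantities or does not exist.

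The size cannot be derived from the documents. On the assumptions in Step 2, the check can report a large gap where there is none, miss a true 8% versus 3% imbalance within a limited band of c, or flag the wrong arm if controls lose more. The result turns on c, which says nothing about missing outcomes.

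A reader might go on to infer that the treatment effects are biased, or that all contrasts among video cells are compromised. The documents support neither. No effect estimate changes directly, and among the 16 cells the problem is small if *viewed* means started. It should be fixed because it concerns the only stated drop-out check for the first main contrast.

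**What to change.** In Section 6.2, define attrition in every arm, including control, as randomised but endline outcome not observed, whatever the exit point. A control who leaves after a recorded endline is then not attrition. Report removals for low quality separately. Test treated versus control, and across the video arms, within each race/ethnicity sample. A table of exit stage by arm would be a useful addition.

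The cost is one sentence and one table. No change to the survey is needed, since assignment already precedes the videos. The downside is a higher reported attrition rate, because losses before viewing and early control losses are now included.
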